5.8 Data Analysis

For Aim 1, the data analysis team will consist of [name], [name], [name], [name] and [name]. [name] will abstract the analytic variable from VINCI-CDW. [name], the biostatistician will work closely with [name] and [name] to create the analytic models

Approach: We will use a combination of traditional epidemiologic studies and machine learning algorithms to determine the long-term, multi-systemic and functional adverse outcomes and/or syndromes related to SARS-CoV-2.

Comparison Groups: We will compare the incidence of long-term outcomes in infected and uninfected Veterans, before vs. after the pandemic and in other potentially informative control groups (e.g. untested Veterans, flu-infected patients.¹⁵)

Unsupervised Machine Learning (ML) Algorithms: We will use ML algorithms to reveal unexpected clusters or patterns of long-term outcomes, which can then be used to generated hypothesis to be tested in more focused statistical analyses. Unsupervised ML analyses will be executed at 6-monthly sequential time points because we anticipate that patterns of long-term complications may vary depending on time since infection.

Regression Analyses: We will build multivariable models (e.g., logit, generalized linear and time to event models) to evaluate associations between SARS-CoV-2 infection and the development of specific long-term outcomes that are either suspected *a priori* (see list below) or suggested by the results of unsupervised analyses. As appropriate, we will also consider approaches such as propensity score matching and instrumental variable analysis to account for measured and unmeasured confounding, respectively.

Adverse Outcomes: We will evaluate outcomes of mortality, hospitalization, readmission, healthcare utilization and costs, days in the community as well as the organ-specific outcomes listed above.

Aim 2 data analyses are described in the study methods.

6. Reporting

As Aim 1 is a secondary analysis of data from VINCI-CDW. The only risk is a potential breach of confidentiality of privacy. This is minimized by keeping the data on password protected VINCI servers at all times. In the unlikely event of a data security incident, we will follow current facility reporting requirements: report (within 1 hour) to the study PI, VA Puget Sound Information Security Officer, Privacy Officer, R&D Associate Chief of Staff, and IRB via the director. Protocol deviations or other violations and non-compliance will be reported according to current regulatory requirements: reported to the IRB within 5 business days of becoming aware of the event.

[name], study Principal Investigator, will report any unanticipated problems, serious adverse events, and protocol deviations to the Ann Arbor VA IRB following local and institutional policies.

7. Privacy and Confidentiality

Aim 1

PHI will be utilized in this data analysis study. This study involves the use of VINCI-CDW data only and no direct contact with participants at any time during the study. The potential risks for harm from this research include those that may result from invasion of privacy or breach of confidentiality.

- 1. Data will always be maintained on VINCI-CDW. Only aggregate data without PII/PHI may be transferred from VINCI. Data will not be shared to anyone outside of the VA.
- 2. Analytic datasets will identify patients only by a study ID number
- 3. Only IRB approved study members will have access to the study data.
- 4. All investigators with access to data will sign the VINCI confidentiality and data use agreement forms and have many years' experience working with these data
- 5. Participants' protected health information will not be disclosed to anyone outside of the approved research team.
- 6. Standard VA data security practices will be in effect at all times, and any breach of VA data security protocol will be reported following VA Puget Sound reporting requirements (see section 6.0 Reporting).

Aim 2

Protected Health Information: we are requesting a HIPAA authorization waiver for the screening portion of this study. We will collect Veteran contact information to contact them for surveys and interviews, as well as social security numbers and medical record numbers. This PHI will only be kept on Microsoft Access behind the VA firewall in a protected folder, here I:\[name] CORC LTO, or on VA REDCap.

Survey Data: Survey data will not contain PHI. This data will be collected via the VA REDCap service by approved study team members. Data will be downloaded on a weekly basis to a protected folder, here I:\[name] CORC LTO.

Interview Data: Interview data may inadvertently contain PHI. This data will be collected by phone and saved on Microsoft Access behind the VA firewall in a protected folder, here I:\[name] CORC LTO, or on VA REDCap.

Veteran PHI will be linked with survey and interview data via a cross walk that links their unique study ID.

We will not disclose PHI to anyone outside of this study, and then only access necessary PHI for the purposes of this study.

Standard VA data security practices will be in effect at all times, and any breach of VA data security protocol will be reported following Ann Arbor VA reporting requirements.

8. Communication Plan

The research team consisting of IRB approved study sites at VA Puget Sound (coordinating center), VA Palo Alto, VA Portland, VA Ann Arbor, and Durham VA will hold regularly scheduled meetings using Microsoft Teams. A study specific team will be set up on Microsoft Teams for the purposes of communication and secure document sharing.

9. Information Security and Data Storage/Movement

VA Informatics and Computing Infrastructure (VINCI)

The VA Informatics and Computing Infrastructure (VINCI) is a Department of Veterans Affairs (VA) Health Services Research & Development (HSR&D) resource center that provides a secure, central analytic platform for performing research and supporting clinical operations activities. It is a partnership between the VA Office of Information Technology (OI&T) and the Veterans Health Administration Office of Research and Development (VHA ORD). VINCI includes a cluster of servers for securely hosting suites of databases integrated from select national VA data

sources. VINCI servers for data, applications and virtual sessions are physically located at the VA Austin Information Technology Center (AITC), located in Austin, Texas. This secure enclave with 105 high-performance servers and 1.5 petabytes of high-speed data storage has multiple layers of security and disaster recovery to prevent data loss.

To ensure the protection of Veteran data, VINCI maintains compliance with the guidelines set forth by Veterans Health Administration (VHA) Handbook 1200.12, Use of Data and Data Repositories in VHA Research, and all other applicable VA and VHA policies and regulations. In addition, VINCI has undergone all security certification activities in support of obtaining an Authorization to Operate (ATO). Access to VINCI resources are approved in accordance with the requirements of National Data Systems (NDS), VHA Handbook 1200.12, Use of Data and Data Repositories in VHA Research, and all other applicable VA and VHA policies and regulations. All data transferred from VINCI is subject to audit for compliance.

VA-credentialed research staffs are granted access to study-specific data along with tools for analysis and reporting in the secure, virtual working environment through a certified VHA network computer within the VA. If not working within a VA or VHA hosted office environment containing VA network access, researchers may apply for and then access VINCI through an approved Virtual Private Network (VPN) and Remote Desktop application. The remote computing environment enables data analysis to be performed directly on VINCI servers, offering a number of advantages: uniform security standards for access; a common point of entry for all investigators who use the data; tools for analysis and reporting; tighter and more consistent control of data quality; and the ability to standardize and update terminology and format as technology and methodology improve.

Data collection

VA provides care to Veterans at over 1,400 points of care. At the core of virtually all care processes is a broadly scoped and extensively used electronic health record system known as the Veterans Information System Technology Architecture (VistA). VistA provides a longitudinal view for patients receiving care nationwide including diagnoses, procedures, medications, labs, physiologic measurements, and text notes and reports. VA uses 130 VistA implementations to provide electronic health record services nationwide for just over 20 million Veterans historically. The aggregate content of these 130 VistA systems includes 2.8 billion documents (e.g., Progress Notes, Discharge Summaries, Reports) accumulating at a rate of 865,000 each day; 7.2 billion lab values (+1.6 million each day), 4.3 billion orders (+949,000 each day), and 4.3 billion medication administrations and prescription fills (+809,000 each day).

Data are aggregated from individual VistA systems to the VA Corporate Data Warehouse where it is modeled and prepared for use. Data published by the VHA Decision Support System (DSS), Inpatient and Outpatient Medical SAS (MedSAS), VA Health Economics Resource Center (HERC) cost data, Vital Status and VA-CMS linked data files maintained by VA Information Resource Center (VIReC), CDC National Death Index VA-linked data, and several other specialty data sets can be requested through VINCI. VA National Data Services (NDS) and other data stewards regulate the right to use the data, but VINCI facilitates the process. When study requests are approved, project-specific data are extracted from source databases and placed in SQL tables accessible only to the research team and VINCI data managers.

Data storage

The study team will keep all sensitive patient data on VINCI project servers maintained by VINCI OI&T personnel and only summarized data without PHI will be downloaded from VINCI to local storage media without data steward permission. Research staff will use an audited VINCI download utility to move summarized data for reports, presentations and publications from VINCI servers to local storage media. The VINCI download utility provides an audit path including a copy of the downloaded material. All study team personnel with access to sensitive patient data will stay current on their VA approved information security training and VA approved privacy policy training. No sensitive patient data will be shared with anyone who does not have a VA appointment.

Data Access

We will use VHA's national electronic medical record (EMR), by way of VistaWeb and JLV.

The only persons having access to the data will be the PIs, the study coordinator and other persons as authorized by the PI. The PI acknowledges that he/she has the ultimate responsibility for security of research study data. OI&T personnel will extract and move study data from VA Corporate Data Warehouse (CDW) source files to the secure VINCI project space allocated to this study by VINCI. OI&T and VINCI personnel not under the purview of the PI will control the servers, network, processors, firewall and software behind the VINCI firewall, including access rights granted to study personnel.

Study data will be kept in accordance with the Department of Veterans Affairs record control schedule 10-1 (RCS 10-1). Upon completion of the research project, the PI in conjunction with the VA Information Security Officer (ISO), and in accordance with VA policy, will ensure that, study data containing sensitive, confidential information will be returned to the VA, sanitized and removed from all servers, desktops, removable storage devices, etc. When any study personnel are no longer a part of the research team, the PI will remove that person's access to all study data and notify the VA Information Security Officer of such action. VINCI personnel will be responsible for maintaining VINCI servers where study data will be kept. It will be VINCI personnel who will move, backup and remove study data from VINCI servers and who will control access to data stored on VINCI servers. The PI will request termination of data access rights for study personnel who are no longer part of the study team.

All study team personnel with access to sensitive patient data will stay current on their VA approved information security training and VA approved privacy policy training. Sensitive patient data will not be shared with anyone who does not have a VA appointment.

Data Storage Location

Study data containing sensitive patient information will be stored on VINCI servers at the Austin Information Technology Center, [name]. The specific server where the data will be stored will be chosen by VINCI personnel. The server name and location within the Austin Information Technology Center may be changed at any time at the discretion of VINCI personnel.

Specialized Software

All software used to access sensitive patient data, whether provided by VINCI, or developed by the study team, will run in virtual desktop sessions on VINCI servers within the Austin Information Technology Center and behind the VINCI firewall.

Sensitive Patient Data on VINCI Servers

Sensitive patient data will not leave the VINCI environment except by explicit permission of the data steward. The data, applications and virtual computing sessions used by the study team reside behind the VINCI firewall in the Austin Information Technology Center. Researchers will use Microsoft Remote Desktop Connection software to access virtual computing sessions from their local workstation. User interface screens are generated on a local workstation but all data processing is done in a virtual computing session on a remote VINCI server. At no time in the data analysis process is data downloaded to local servers or workstations. Sensitive patient data may appear on the local screen but it is not stored on the local workstation. When the user logs out of the virtual session, no trace of the sensitive data will be available at the local workstation. Microsoft Remote Desktop Connection software uses a VA-approved secure communications protocol between the local workstation and the remote VINCI server. There is no World Wide Web access from servers behind the VINCI firewall.

All study data containing PHI or other sensitive patient data in electronic format or in paper format whether stored on VA or non-VA equipment will be maintained on password protected and encrypted computers or on VA REDCap, behind locked doors, in a secured building. No sensitive patient information will be included in any

unencrypted, character-based communication between study team members or with other VA or non-VA personnel. Study team members with access to sensitive patient data on VINCI will all have the same data access rights and restrictions.

Data Repository

Statistical Analysis Plan

COVID-19 Observational Research Collaboratory
NCT05394025

Updated: June 25, 2025

Background

In a previous study, we found Veterans with a first case of COVID-19 (between 2020 and 2021) did not report more limitations in instrumental activities of daily living (IADL) at 18-months after infection relative to comparators who were contemporaneously uninfected.

Aim

In this updated longitudinal analysis, we examine whether self-reported counts of IADL changed between infected and uninfected comparators over 18 additional months of follow-up (36 months after infection).

Study Design

Prospective cohort study design with repeated surveys at 18-, 24-, 30-, and 36- months.

Population

The cohort was sampled from a parent cohort of Veterans, assembled by the COVID-19 Observational Research Collaboratory, with a first documented case of COVID-19 between March 2020 and April 2021 and uninfected matched comparators. Veterans were required to have been enrolled in VHA care, been assigned a VA primary care team, and had one or more VA primary care visits in the two years prior to cohort construction. COVID-19 infections were ascertained through the VA COVID-19 Shared Data Resource (CSDR) and Medicare claims data. Otherwise, eligible Veterans without evidence of a documented infection were considered as uninfected comparators. From this parent cohort, we conducted a stratified random sample of 100 Veterans who tested positive for COVID-19 in October, November, December, February, March, and April 2021. Sampling was further stratified by US Census region and hospitalization status. Of the 600 patients with COVID-19 a total of 235 (39.2%) Veterans consented and completed surveys; 244 uninfected matched comparators completed surveys.

Exposure

First documented COVID-19 infection (positive PCR test or clinical note) was the primary exposure of interest. Veterans without a documented history of COVID-19 infection were eligible comparators. Extensive matching, done monthly, was used to ensure comparability between groups.

Outcome

Self-reported IADL limitations were the primary outcomes of interest. The IADL instrument was initially administered at 18-months after infection (or matched index date) and was subsequently readministered three additional times 6 months apart. The IADL asks respondents whether they experienced difficulties or limitations with daily activities and functions such as with "walking across a room" or "shopping for groceries." We report individual IADL responses but use a cumulative count of self-reported limitations (0-14) as our primary IADL score as an outcome.

Analysis

We used descriptive statistics to compare the Veterans with COVID-19 and comparators. A table of frequencies was generated to compare IADL item responses between groups at each time point. We used a linear mixed model with random intercept (respondent) and slope (survey cycle time) to assess differences in the change in IADL scores. The model included terms for age, sex, and Care Assessment Needs (CAN) score to adjust for potential important confounders. An interaction term between COVID-19 status and time was included to assess whether changes in IADL scores over time differed between the COVID-19 and comparator groups. We used a likelihood ratio test to test for statistical significance and report 95% confidence intervals for all reported model coefficients.

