A driving finding in VA research for the last decade has been that there is unequal and incomplete access to the benefits of VA care. EHR data by definition are only available for Veterans who have accessed care in the VA, including VA community-based care and contracted care. Other Administrative data (e.g., claims data for Medicare, Medicaid) are not available in real-time, given our dependency on other entities (i.e., CMS and VIReC) for production and linkage. Further, many important measures are not systematically ascertained or entered into the EHR in a uniform fashion for all patients. Therefore, prospective primary data collection from Veterans is necessary to define measures that are poorly captured in the VA EHR including care received at non-VA sites, caregiving receipt, disability, and employment/role function and financial toxicity, and unmet care needs in order to ensure the relevance of the work being done here. In general, we will seek to survey Veterans at 12, 18, 24, 30, and 36 months after their initial SARS-CoV-2 infection, enrolling new patients as the epidemic continues, and following patients longitudinally. The key variables of interest from new survey data for the LTO are shown in Table 2 below.

Concept	Instrument	# of items (Approx)			
Activity + Quality of Life	Activities of Daily Living (ADL) and Instrumental Activities of Daily Living (IADL); EQ-5D-5L	18			
Participation	Life Space Mobility	9+			
Employment	Health and Retirement Study's Job Status Form	1			
Financial Toxicity	NHLBI COVID-19 Financial Toxicity scale	10			
Mental Health	PHQ-9 Depression Symptoms scale	9			
Unmet Need	PROMISE instrumental support	4			
Non-VA Healthcare	VIREC Utilization Measures	2			
Fatigue + Symptoms	PROMIS Fatigue Short Form 7a; open-ended questions	9			

Aim 2 Study Population: The population of Veterans eligible for random sampling into the survey will be the same as those eligible for inclusion in Aim 1. Therefore, all data from Aim 1 will be linkable to survey responses via a cross walk.

Cases: Our primary case definition are Veterans infected with SARS-CoV-2, as defined by the standard locally available test at the time of their infection, and identified within the COVID-NST. We will restrict to Veterans seeking primary care in VA. Viral infection index date will be defined as the date of sample collection for each

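### The SAP's 0-14 primary 'IADL' score appears to mix basic ADL items with instrumental ones, so a result on it cannot be attributed specifically to instrumental activities

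*SAP*

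**What the plan says.** The SAP's Background spells the construct out as instrumental activities of daily living and reports an earlier null finding on it at 18 months. The Aim continues on the same construct: "we examine whether self-reported counts of IADL changed between infected and uninfected comparators over 18 additional months of follow-up".

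Under Outcome, the SAP says "Self-reported IADL limitations were the primary outcomes of interest". It describes the instrument through two examples. The first is "walking across a room"; the second is "shopping for groceries". The score is set there: "We report individual IADL responses but use a cumulative count of self-reported limitations (0-14) as our primary IADL score as an outcome".

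Under Analysis, this score goes into a linear mixed model with random intercept and slope. The COVID-by-time interaction carries the question. A table of item frequencies by group and time point accompanies it.

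In the protocol, section 5.1, Table 2, one row names the instruments as "Activities of Daily Living (ADL) and Instrumental Activities of Daily Living (IADL); EQ-5D-5L", with about 18 items for the row. The Introduction lists the Aim 2 primary outcomes and includes disability. It does not single out IADL.

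Neither document lists the 14 items, classifies them as ADL or IADL, or defines subscores.

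**The concern.** The SAP uses one label, IADL, for the construct, the question and the score, and does not name basic ADL anywhere. Yet the first of its two example items is a mobility item that is conventionally a basic ADL. The protocol keeps the two domains apart by name.

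The label governs what the primary analysis may conclude. If the interaction is null, the natural report is that change in IADL did not differ between groups. If it is positive, the natural report is an IADL effect. On a mixed count neither statement follows: the total can move because of either domain, and change in one can be masked by noise from the other. If the 18-month result in the Background used the same count, the mislabelling would extend to that statement too. The SAP does not say whether it did.

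**Working it through.** **1. Does the score contain a basic ADL item?** The SAP's two examples are "walking across a room" and "shopping for groceries". By convention the first is a basic ADL and the second an IADL. That classification is not in the documents. It puts at least one ADL-type item in the score.

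**2. Does the length fit a combined battery?** A count of limitations from 0 to 14 implies 14 items worth one point each. Table 2 gives about 18 items for ADL, IADL and EQ-5D-5L together. The split is not given. Assuming 5 or 6 items for EQ-5D-5L:

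- 18 − 5 = 13, or 18 − 6 = 12, left for ADL plus IADL.
- If all 14 items were IADL, 18 − 14 = 4 would remain for ADL and EQ-5D-5L together, fewer than EQ-5D-5L alone needs under this assumption.

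Neither 12 nor 13 equals 14, but the column is marked approximate. The combined reading is off by one or two items. The IADL-only reading leaves no room for ADL at all. This is suggestive, not proof.

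**3. What could pooling do to the analysis?** The SAP attaches no power, alpha, SD or effect size to this outcome, so there is no planned figure to reproduce. The following is an illustration.

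From the SAP: 235 COVID-19 respondents, 244 comparators, 14 items. Assumed: two-sided alpha 0.05; a true effect of 0.25 SD on one subscore and none on the other; k ADL items; subscore correlation ρ = 0.5 to 0.85; per-item SD ratio (ADL:IADL) r = 0.5 to 1.0. It compares means at one time point, which simplifies the SAP's slope comparison.

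Formulas, with S_I = 14 − k and S_A = k·r in arbitrary units:

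- S_T = √(S_I² + S_A² + 2ρ·S_I·S_A)
- IADL-only effect seen on the total: d = 0.25·S_I/S_T
- ADL-only effect seen on the total: d = 0.25·S_A/S_T
- SE = √(1/235 + 1/244) = 0.0914; power = Φ(d/SE − 1.96)

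On an IADL-only score: 0.25/0.0914 = 2.735, and Φ(2.735 − 1.96) = 78.1%.

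Example with k = 7, ρ = 0.7, r = 1: S_T = √(49 + 49 + 68.6) = 12.91; d = 0.25 × 7/12.91 = 0.136; power = 31.7%.

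Ranges over ρ and r:

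| ADL items of 14 | IADL-only effect: SD on total | Power on total | ADL-only effect: SD on total |
|---|---|---|---|
| 1 | 0.234–0.245 | 72.8–76.5% | 0.009–0.018 |
| 3 | 0.202–0.233 | 59.7–72.1% | 0.030–0.059 |
| 6 | 0.148–0.203 | 36.8–60.3% | 0.070–0.123 |
| 7 | 0.130–0.189 | 29.5–54.3% | 0.086–0.144 |

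With seven ADL items, an effect confined to ADL has up to 35% power on the total and would be reported as an IADL effect.

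**4. What if both domains are affected?** With the same standardized effect on both subscores, the total shows (S_I + S_A)/S_T times that effect. For k = 7:

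- ρ = 0.5, r = 1: 14/√147 = 1.15
- ρ = 0.85, r = 0.5: 10.5/√102.9 = 1.04

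Pooling then costs nothing and slightly helps.

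**The case against.** The strongest reply is that the SAP defines its count openly, examples included, and that a combined count is a sound measure of disability, which the protocol names as a primary outcome. The SAP also reports every item by group and time point, so a reader can see where differences lie. Only one ADL-type item is shown. Protocol section 5.1 allows items to be considered for replacement over time, so Table 2 cannot fix the content of the SAP's score.

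Much of this stands. It is a reason to keep the total as primary and to treat the item arithmetic as indirect evidence. It does not remove the mismatch between label and content. The frequency table is descriptive and unadjusted; it does not test whether change over time differs between groups, which is the stated question. Measuring disability well is also different from supporting a statement about instrumental activities.

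A reader might go further and infer that the score fails to answer the SAP's question, or that a known share of the effect is lost. The documents do not support either. The score does contain instrumental items, the split of the 14 is not given, and dilution arises only if the effect is concentrated in one domain.

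**Conclusion.** The concern holds in limited form. The primary score appears to combine ADL and IADL items under an IADL label, so a result on it supports a statement about ADL/IADL limitations, not about instrumental activities specifically. This rests on the conventional classification of one example item, on the approximate Table 2 count, and on an assumed 5 or 6 EQ-5D-5L items.

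The size of any loss is unknown. In the illustration it runs from trivial (78% to 73–77% power with one ADL item) to substantial (30–54% with seven), and it disappears when both domains are affected. Every input except the sample sizes and the 14 items is assumed, and a slope comparison would also depend on variance components that the SAP does not give.

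It would also be wrong to infer that the earlier 18-month finding is unsound. The SAP does not say which count that analysis used.

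**What to change.** - List the 14 items in the SAP and classify each as ADL or IADL.
- Rename the total an ADL/IADL limitation count throughout. Keep it as the primary outcome and tie it to the protocol's disability outcome. Amend the Background statement too if the 18-month analysis used the same count.
- Fit the same mixed model, with the same covariates and interaction, to the IADL subscore and the ADL subscore. Label both as secondary or sensitivity analyses.
- Word conclusions from the total as ADL/IADL limitations. Rest any IADL-specific statement on the IADL subscore and mark it as secondary.

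The cost is SAP wording and two further runs of an existing model on responses already collected. The downside is two more secondary estimates. Because the SAP describes its analyses in the past tense, they may be post hoc and should be labelled so if they are.
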